dispensing data. During the visit, parents and adolescents will receive training on how to use mehealth for ADHD and will choose one of the five medication experiments to complete together and track the effects for the desired amount of time. Once dyads have completed the medication experiment, they will complete a follow-up study visit to review the results from the experiment, discuss feasibility of the software, and complete end of study measures.

Figure 2.

^{*}Electronic baseline surveys: Demographics, Health-Care Literacy Scale, Vanderbilt Scale/ADHD Self-report, Columbia Impairment Scale, Pittsburgh Side-Effect Rating Scale, Pre-Intention Factors, Medication Barriers, Behavioral Intention, Conflict Behavior Questionnaire, and (adolescents only) Medication Diversion

DURATION:

This IRB protocol covers the phase of the study during which we will test the medication experiment feature developed in collaboration with our stakeholders during the first phase of the study. Families can customize the start and end date as well as the amount of time they track effects in the medication experiment. Thus, families could be enrolled in the study for up to 4-

months. We expect that all 30 dyads will be recruited and complete the study participation over the course of one year.

PROCEDURES:

Research Participant Recruitment and Obtaining Informed Consent

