At the conclusion of the medication experiment, the research assistant will schedule an inperson study visit at the Center for ADHD. The study physician, adolescent and parents will discuss what was learned using a report generated by mehealth for ADHD to visualize the outcome data that was collected. Subsequently, the adolescent and parent will be asked to independently indicate their preference for what to do next (continue [medication regimen from experiment], resume previous medication/dosage, conduct another experiment, return to pediatrician to adjust dosage or change medication, other), and their preferred role in decision-making. The study physician will then facilitate a discussion to resolve any differences between adolescent and parent preferences and come to a consensus. The parent will receive a study summary document to share with their child's pediatrician so s/he is aware of what was learned and can use this to guide future management decisions. The adolescent and parent will report this decision, their certainty about the decision, their preferred role in decision-making, their involvement in the process of making this decision, and their intentions about taking/giving medicine. We will also ask the parent and adolescent about the usability the medication experiment software (see Measures).

Measurement Strategy: Aggregation of individual trials to estimate a population level treatment effect isn't needed given the strong evidence of stimulant effectiveness among adolescents.¹ Rather, it is important to ascertain whether the use of medication experiments helps adolescents and parents work together to resolve uncertainty about future use of medicine. We will describe the type and number of medication experiments conducted as well as the personal outcomes selected for tracking. We will examine process outcomes like the decision-making involvement, comfort with the decision made, and whether the decision was implemented.

Measures to characterize the sample on demographic, ADHD, and psychosocial factors

- 1. Demographics: Adolescents, parents, and pediatricians will report on age and race/ethnicity. Parents will also report on child insurance status, and their own level of education and mental health history.

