- 13. Certainty about the decision will be measured using the Decisional Conflict Scale (DCS): The DCS⁷⁰ has an initial question to ascertain the option that has been selected. Options presented will be: continue [medication regimen from experiment], resume previous medication/dosage, conduct another experiment, return to pediatrician to adjust dosage or change medication, other [write in]. The DCS then has 16 questions that are divided into five subscales: informed subscale, values clarity subscale, support subscale, uncertainty subscale, and an effective decision subscale. The informed subscale measures how informed participants feel about the benefits and risks of the decision. The values clarity subscale measures a participant's feelings about personal values for benefits and risks/side effects. The support subscale measures perceived levels of support during decision-making. The uncertainty subscale measures a participant's level of certainty about the best choice to make. The effective decision subscale measures the satisfaction with the decision made. The total DCS score equally weighs all five subscales. Responses to each question are reported on a 5-point Likert scale (0 = strongly agree to 4 = strongly disagree). The total DCS scores are calculated by summing item scores and then converting the scores to a 0-100 scale, where 0 implies no decisional conflict and 100 implies extremely high decisional conflict. Scores <25, 25 to 37.5, >37.5 indicate low, moderate and high decisional conflict, respectively. Scores 25 and higher reflect clinically significant decision conflict.
- 14. Behavioral Intention questions that will assess the adolescent and parent intention to take/give ADHD medicine regularly will be measured using the standard measure of intention from the UTBC. 46 Responses are on a 7-point scale from strongly agree (+3) to strongly disagree (-3) that assess intention to take medicine for ADHD on weekdays, weekends, and school vacations.
- 15. System Usability Scale (SUS)⁷¹ is a validated 10-item unidimensional scale with response options on a 5-point agreement scale which results in a score from 0 to 100, with higher scores indicating greater usability.

Implementation of decision: 3 months after study visit 2, we will obtain pharmacy dispensing records to ascertain whether their joint decision was implemented. If medication was continued, we will calculate the percentage of days covered.

DATA ANALYSIS

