We will conduct descriptive analyses to summarize measures that characterize the sample in terms of demographic, ADHD, and psychosocial factors, the experiments selected, and decisions made, as well as feasibility and usability data. In order to determine overall feasibility and usability of our pilot intervention, we will compare retention, participation, and usability ratings to a priori criteria based on previous research (i.e., retention $\geq 80\%$, participation $\geq 80\%$, usability ≥ 70), 72 using Chi-square tests.

Power and Sample Size

We selected a target sample size of 30 to exceed the recommended sample size (n = 20) for a pilot trial designed to inform a larger efficacy trial with 80% power to detect a medium effect. Of note, we aren't powering the study to examine differences in outcomes by experiment type. Paired-samples t-tests will be used to calculate the change in DMIS,DCS, and behavioral intentions for all adolescents and parents, and for medication continuity among the subset who choose to continue medication after completing their experiment. Cohen's d will be calculated to estimate effect size for each pre- to post-outcome and interpreted as small (.20), medium (.50), and large (.80).

Hypothesis testing

We will test the following hypotheses:

- 1. From pre to post, within-subject report on DMIS subscales "child express" will increase and "parent seek" will increase.
 - a. Paired sample t-test
- 2. From pre to post, within-subject DCS will decrease.
 - a. Paired sample t-test
- 3. Higher post-DMIS joint/decision scores will be reported by dyads who differ on initial preferences following the experiment compared to those who don't.
 - a. Two sample t-test
- 4. Higher post-child express scores will be reported by adolescents who want to make the decision alone compared to those who prefer to share decision or have parent make decision.
 - a. Two-sample t-test
- 5. Adolescent-parent conflict as measured at baseline by the CBQ will be positively associated with discordance in independent preferences following the medication experiment.
 - a. Biserial correlation coefficient
- 6. The difference between the adolescent's intention to take ADHD medication and the parent's intention to give ADHD will decrease from pre to post.
 - a. Linear mixed model

Scientific Rigor:

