There will be no costs to the subject for participating in this study. The study physician will provide prescriptions, as needed, during trial participation, but participants will be responsible for obtaining ADHD medication from their pharmacy as they do for typical clinical care.

PAYMENT FOR PARTICIPATION

Each parent/adolescent dyad will be compensated \$50 for survey completion and \$100 for completing each study visit. They will additionally receive up to \$100 for time spent submitting data during the medication experiment . This will be pro-rated based on the % of days with complete data reported over days expected. For example, if the medication experiment lasts for 6 weeks and both parent and adolescent entered data for 34 out of the 42 days, they would receive 80.9% of \$100 = \$80.90. Therefore the maximum total compensation throughout the study is \$350.

References

- 5. [name] WB, Sherman SN, Zmitrovich AR, et al. In their own words: adolescent views on ADHD and their evolving role managing medication. Research Support, N.I.H., Extramural Research Support, Non-U.S. Gov't. *Acad Pediatr*. Jan-Feb 2012;12(1):53-61. doi:10.1016/j.acap.2011.10.003
- 6. Pliszka S. Practice parameter for the assessment and treatment of children and adolescents with attention-deficit/hyperactivity disorder. *J Am Acad Child Adolesc Psychiatry*. Jul 2007;46(7):894-921.

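### The chi-square test named for usability has no null value for a 0-100 SUS score judged against 70, so it cannot be run as written; the participation criterion also needs a definition

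*Combined protocol and SAP*

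**What the plan says.** Under DATA ANALYSIS, the combined protocol and SAP states how overall feasibility and usability will be determined: "we will compare retention, participation, and usability ratings to a priori criteria based on previous research". The thresholds are 80% for retention, 80% for participation and 70 for usability. One method is given for all three, "using Chi-square tests". The same paragraph plans descriptive analyses of the sample, the experiments and the decisions, "as well as feasibility and usability data".

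Usability is measured by the SUS (Outcome Measures, item 15), a ten-item scale "which results in a score from 0 to 100, with higher scores indicating greater usability". Both members of the dyad rate it at the follow-up visit, according to the last part of the Intervention section: "We will also ask the parent and adolescent about the usability the medication experiment software".

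Participation as a criterion appears only in the DATA ANALYSIS sentence. The closest related text is the payment rule under PAYMENT FOR PARTICIPATION: "This will be pro-rated based on the % of days with complete data reported over days expected". Its worked example supposes that "both parent and adolescent entered data for 34 out of the 42 days". That section does not mention the 80% criterion, and DATA ANALYSIS does not mention the payment rule.

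**The concern.** A one-sample chi-square test compares observed counts in categories with the counts expected under a stated proportion. Retention supplies both: dyads retained or not, against 80%. Usability supplies neither directly. Each rater gives a score, and 70 is a point on the score scale, not a proportion of raters. The test becomes possible only if raters are split at 70 and a target share at or above 70 is fixed. The plan gives the 70 but no share. It also does not say whether adolescent and parent ratings are pooled, averaged or judged separately.

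Feasibility and acceptability are stated aims (PURPOSE OF STUDY; Scientific Rigor), and this sentence is the plan's route to a conclusion on usability. As written, the analyst would choose the missing share, or switch to the mean, after the scores are in.

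Participation raises a lesser question: 80% of what, and counted per person, per dyad or per day?

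**Working it through.** The three thresholds have no calculation behind them, so there is no figure of the plan's to reproduce for usability. The only related arithmetic is the payment example: 34/42 = 80.95%, which agrees with the stated 80.9% after truncation.

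**Inputs from the documents:** 30 dyads; SUS range 0-100; usability threshold 70; two raters per dyad; retention and participation thresholds 80%.

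**Inputs not in the documents, assumed here:** SUS standard deviation 10, 15 or 20; two-sided alpha 0.05; target shares of 50%, 70% and 80%, used only to show dependence on the missing number.

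**1. The mean and the share can disagree.** No distribution is assumed; each line is a possible set of 30 scores.
- 12 scores of 100 and 18 of 65: mean = (1200 + 1170)/30 = 79, above 70; share at or above 70 = 12/30 = 40%.
- 24 scores of 72.5 and 6 of 40: mean = (1740 + 240)/30 = 66, below 70; share at or above 70 = 24/30 = 80%.

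**2. If raters are split at 70, the verdict depends on the unstated share.** With x of 30 raters at or above 70 and null share p, chi-square = (x − 30p)²/(30p) + (x − 30p)²/(30(1 − p)), against a critical value of 3.84.
- p = 50%: x = 21 gives 36/15 + 36/15 = 4.80 (significant); x = 20 gives 25/15 + 25/15 = 3.33 (not).
- p = 70%: x = 26 gives 25/21 + 25/9 = 3.97 (significant); x = 25 gives 16/21 + 16/9 = 2.54 (not).
- p = 80%: x = 29 gives 25/24 + 25/6 = 5.21 (significant); x = 28 gives 16/24 + 16/6 = 3.33 (not).

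So 21, 26 or 29 raters of 30 are needed to be significantly above target, according to a number that the plan does not give.

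**3. What the mean would deliver.** The half-width of the 95% interval is t(0.975, n − 1) × SD/√n.

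| Raters of one type | SD 10 | SD 15 | SD 20 |
|---|---|---|---|
| 30 (t = 2.045) | 3.7 | 5.6 | 7.5 |
| 24 (t = 2.069) | 4.2 | 6.3 | 8.4 |

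The second row matters because usability is asked at the follow-up visit: at 80% retention, 0.80 × 30 = 24 raters of each type remain.

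**4. Participation.** The definition can move the result across 80%. If parents completed 90% of days and adolescents 85%, independently (assumed), each would pass, but days with both complete would be 0.90 × 0.85 = 76.5%, which fails. The payment example requires both members to have entered data.

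**5. Retention.** At 30 dyads the expected counts under 80% are 24 and 6. A chi-square test can be used here.

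**The case against.** The best defence is that the plan compares usability ratings with a threshold by chi-square, which fits the share of raters scoring at least 70 as well as it fits a mean. On that reading the test is usable and one number is missing. Much of this stands: the documents never make the mean the target, and a reader who infers that the cut at 70 must be invented would be wrong, because 70 is stated. What remains is that the test has no null proportion, and the two raters are not dealt with. The cited source for the criteria cannot be consulted, and the protocol itself states no rule.

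A reader might also infer that chi-square is wrong for all three criteria. It is not: it suits retention, and would suit participation if dyads were counted as participating or not.

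A third tempting inference is that the plan will pool tracking days across dyads and so inflate its error rate. No section proposes pooling. The only related text computes a percentage within each dyad, and counting dyads is an equally simple reading. Participation is therefore a missing definition, not a demonstrated error.

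Finally, this is a 30-dyad single-arm pilot, descriptive summaries of usability are already planned, and no section ties a stop or go decision to the thresholds. That limits the harm. It does not tell anyone how the usability criterion is to be judged.

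**Conclusion.** The point holds for usability: the named test lacks the null share it needs and cannot be carried out from the plan as written. This conclusion follows from the text and needs no assumption. That the choice of reading can reverse the verdict is shown by the two constructed score sets, which demonstrate possibility and not likelihood; the documents give no information on the spread or shape of SUS scores. The interval widths rest on an assumed SD of 10 to 20, and the counts of 21, 26 and 29 on an assumed two-sided 5% level.

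For participation the conclusion is weaker: the numerator and unit are unstated and should be supplied. The retention test is not faulted. The consequence is moderate, since usability will be described in any case, but the gap should be closed before any usability data are examined.

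**What to change.** In DATA ANALYSIS, restrict the chi-square wording so that it no longer covers usability, and add:

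- **Usability.** Compare the mean SUS with 70 and report a one-sample t 95% confidence interval, separately for adolescents and parents because their scores are paired within dyads. Name in advance which rater's mean decides the criterion; report the other alongside.
- **Participation.** State the numerator, denominator and unit. If the payment rule's percentage of complete days is meant, calculate it for each dyad, compare the mean across dyads with 80%, and give a 95% interval with the dyad as the unit. Do not pool days: days from one dyad are not independent, and because "Families can customize the start and end date as well as the amount of time they track effects in the medication experiment", pooling would weight longer experiments more heavily (a 42-day experiment would count 42/28 = 1.5 times a 28-day one).
- **Retention.** No change to the test is needed.

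The cost is two or three sentences and two decisions, with no new data, visits or participants. The drawback is limited precision. With 30 raters, an observed mean of exactly 70 would carry an interval of 66.3 to 73.7 at SD 10 and 62.5 to 77.5 at SD 20, and wider still if only 24 raters attend the follow-up visit. Meeting the criterion on the mean would therefore not show that true usability exceeds 70, and the report should say so.

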[name] developed a web-based intervention (mehealth for ADHD) which enables community-based pediatricians to deliver higher quality ADHD care⁴⁴ leading to children with significantly fewer ADHD symptoms. 45 Subsequently, partnerships with the American Academy of Pediatrics and American Board of Pediatrics helped spread use of the portal beyond practices that participated in research and now includes 60,801 patients cared for by 2,153 pediatricians in 886 practices across the US. These practices use the portal as a registry to manage their entire ADHD patient population. With pediatricians continuing to enroll patients on the portal as part of routine clinical care, opportunity exists to leverage this infrastucture to efficiently develop and test new interventions. The proposed research would fill a sizable gap as the current portal is focused exclusively on young school age children with ADHD and medication adherence has not been targeted nor improved. Specifically, while a randomized controlled trial testing the efficacy of the mehealth for ADHD web intervention demonstrated significant effects on children's treatment outcomes, there was not a significant intervention effect on medication adherence (i.e., 59% of days covered by children in the mehealth for ADHD portal group vs. 54% in the control group). 45 Moreover, the portal is devoid of features for adolescents. In focus groups, pediatricians, parents, and adolescents have repeatedly requested such features.

STUDY DESIGN:

We will conduct a pilot, single-arm, open-label trial of the medication experiment feature among 30 adolescents experiencing uncertainty about continued medicine use (see **Figure 2**). Because the medication experiment feature is not clinically relevant for adolescents taking a non-stimulant ADHD medication, they will be excluded. At the time of enrollment, families will complete baseline measures electronically and schedule an in-person visit. We will verify the medication prescribed and the number of days covered with medicine in the past year using

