All participants will be recruited from Cincinnati Children's Hospital. We will advertise the study to CCHMC employees via flyers and emails to recruit their eligible adolescents to participate. Parents will be able to contact the research team to receive additional information. Those who express interest will complete screening questions needed to verify eligibility criteria. If they are eligible, the research assistant will review the full electronic consent and assent forms with the parent and adolescent via phone call. After we review the content of the consent form with the parent, they will record their consent on REDCap using a study-specific consent form modeled after the eConsent demo on the REDCap Resource Center. We will also explain the study to adolescents (in language appropriate to them; see below), and document their assent in REDCap. Once 30 dyads have been consented and enrolled, parents that filled out the interest form that were never called by the study team will be sent a blind carbon copy email via REDCap that explains that the target participant goal has been met and they will be put on a waitlist in the case of participant attrition. They will also be contacted at study completion to inform them that the study is no longer recruiting.

Inclusion/Exclusion Criteria

Inclusion Criteria: Participants for the study must meet all of the following criteria:

- a. Consent: A parent or legal guardian must provide written informed consent
- b. Assent: Adolescents must provide written assent to participate in the study
- c. Ages 11-15
- d. Treated for ADHD by pediatrician
- e. First prescribed ADHD medicine more than one year prior to enrollment
- f. Filled at least one prescription for a stimulant medication in the past year
- g. Uncertainty about continued ADHD medication use
- h. Only one child per household can participate in the study. For families who have more than one child who is potentially eligible, they may decide which of their children would be the best fit for the study.

Exclusion Criteria: Participants will be excluded from the study if they meet any of the following criteria:

- a. Do not have reliable access to the internet at their home or another location.
- b. Will not permit their child to access the internet for study related activities.
- c. Are not able or willing to send or receive text messages.

Intervention

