An open label trial is an appropriate design to test the feasibility, acceptability, and preliminary efficacy of the medication experiment intervention and therefore warrants further testing in a future larger trial. Our preliminary data strongly supports the importance of the problem, intervention targets identified, and the feasibility of the approach in our hands.

FACILITIES

Cincinnati Children's Hospital Center for ADHD is the performance site for this study.

POTENTIAL BENEFITS

Although we cannot guarantee a benefit to any individual participating adolescent or parent, medication experiments are recommended in clinical practice guidelines to help resolve uncertainty about continued medication use. Benefits of the study outweigh any potential risks because this intervention will likely improve care.

POTENTIAL RISKS, DISCOMFORTS, INCONVENIENCES, AND PRECAUTIONS

There is minimal risk to the participants in this study. For dyads who select a medication experiment involving not taking medicine for some period of time, it is possible the adolescent could experience more ADHD symptoms than usual and/or a decline in functioning. Indeed, adolescents often experience such effects when conducting impromptu experiments without physician supervision. For dyads who select a medication experiment involving taking medication on additional days (e.g., non-school days) or trying a different medication or dosage, it is possible the adolescent could experience side effects which s/he may or may not have experienced in the past. Both of these scenarios are the reason why clinical practice guidelines recommend that medication experiments are personalized, structured, and physician supervised. Dyads will be able to reach the study team between visits with any concerns. Medication experiments will end early if needed.

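### The chi-square test planned for the 80% retention criterion does not show whether the criterion was met: at 30 dyads and an assumed two-sided 0.05 level it is non-significant from 67% to 93% retention

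*Combined protocol and SAP*

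**What the plan says.** The Study Design section describes a "single-arm, open-label trial of the medication experiment feature among 30 adolescents", so there is no comparator. The Data Analysis section promises descriptive summaries that include feasibility and usability data. The purpose of the step that follows is given as "In order to determine overall feasibility and usability of our pilot intervention". The step itself reads "we will compare retention, participation, and usability ratings to a priori criteria based on previous research". The criteria are retention of at least 80%, participation of at least 80% and a usability rating of at least 70, and the comparison is to be made "using Chi-square tests".

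For this comparison the plan states no significance level, no direction, no rule linking the result to the criterion, and no confidence interval. Retention is not defined. The sample size of 30 is justified as exceeding a recommended pilot size of 20, not by reference to this test. The recruitment section adds that once 30 dyads are enrolled, interested families who were never called are told that "they will be put on a waitlist in the case of participant attrition", so more than 30 dyads could eventually be enrolled.

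**The concern.** The criterion runs in one direction: retention either reaches 80% or it does not. A chi-square test against 80% treats a shortfall and an excess alike. With so few dyads it also returns the same non-significant result over a wide range on both sides of the threshold. Since the plan does not say how the p-value bears on the criterion, the link would have to be chosen later, possibly after the data are seen. Feasibility is one of the stated purposes of this pilot and retention is one of three measures used to judge it, so the comparison should give a clear answer.

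**Working it through.** **Inputs.** The criterion of 80% and the chi-square test come from Data Analysis; 30 dyads in a single arm come from Study Design and Power and Sample Size. With one arm and a fixed criterion, the natural reading is a one-sample goodness-of-fit test with 1 degree of freedom. The significance level is not stated. I assume two-sided 0.05 and show other choices below.

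**The plan's own figure.** The plan gives no power, level or critical count for the retention comparison, so there is nothing to reproduce.

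**Test statistic.** At 80%, the expected counts are 24 retained and 6 lost. For k retained,

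X² = (k − 24)²/24 + (k − 24)²/6 = (k − 24)²/4.8.

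For example, k = 20 gives 16/4.8 = 3.33 and k = 19 gives 25/4.8 = 5.21.

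| Retained of 30 | Rate | At least 80%? | X² | p | Exact 95% interval |
|---|---|---|---|---|---|
| 19 | 63.3% | no | 5.21 | 0.022 | 43.9% to 80.1% |
| 20 | 66.7% | no | 3.33 | 0.068 | 47.2% to 82.7% |
| 22 | 73.3% | no | 0.83 | 0.36 | 54.1% to 87.7% |
| 24 | 80.0% | yes | 0 | 1.00 | 61.4% to 92.3% |
| 27 | 90.0% | yes | 1.88 | 0.17 | 73.5% to 97.9% |
| 28 | 93.3% | yes | 3.33 | 0.068 | 77.9% to 99.2% |
| 29 | 96.7% | yes | 5.21 | 0.022 | 82.8% to 99.9% |

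Every count from 20 to 28 is non-significant. Counts 20 to 23 miss the criterion and counts 24 to 28 meet it. Outside the band the p-value alone does not show the direction: 19 and 29 share p = 0.022.

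**Other choices of test and level.**
- Continuity correction: same band (p = 0.110 at 20 and 28; 0.040 at 19 and 29).
- Exact two-sided binomial: same band (19: 0.036; 20: 0.105; 28: 0.070; 29: 0.020).
- Two-sided 0.10, uncorrected: band 21 to 27 (70% to 90%).
- One-sided 0.05 for exceeding 80%: needs 28 of 30 (score p = 0.034, exact p = 0.044).
- One-sided 0.05 for falling below 80%: rejects at 20 or fewer by the score test (p = 0.034), and at 19 or fewer by the exact test (20 gives p = 0.061).
- Denominators of 28 to 32: the two-sided 0.05 band stays at about 66% to 94%.

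**How often the result is uninformative.** With K binomial (30, π), the chance that K falls between 20 and 28 is 0.73 at π = 70%, 0.89 at 75%, 0.96 at 80%, 0.95 at 85% and 0.82 at 90%.

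**The simple rule for comparison.** The chance that K is at least 24 is 0.16 at π = 70%, 0.35 at 75%, 0.61 at 80%, 0.85 at 85% and 0.97 at 90%.

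**The case against.** The strongest reply is that the plan already contains a usable rule. The criterion is a numeric threshold fixed in advance, and the same section commits to describing the feasibility data. A rate of 20/30 would be seen to fall short of 80% whatever the p-value. This largely stands: the weakness lies in the test, and the plan as a whole does not hide the answer. What remains is that the test is the only stated means of comparison and nothing says that the observed rate decides.

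A second reply is that the 67% to 93% band depends on an assumed level. That is correct. Under a one-sided 0.05 reading 28/30 is significantly above 80%, and at two-sided 0.10 the band narrows. Some wide indeterminate band survives under every reading tried.

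A third is that much of the width comes from having 30 dyads. This also stands. The exact 95% interval contains 80% for every count from 19 to 28, slightly wider than the test's own band. An interval gains nothing in precision; it shows the imprecision openly and leaves the verdict to the observed rate.

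Three stronger readings are tempting.
- A reader might infer that the plan would pass a pilot that lost a third of its dyads, or fail one that kept 90%. The documents do not say that non-significance counts as meeting the criterion, nor that significance is required to meet it.
- A reader might infer that the verdict is prejudged, because the Purpose and Scientific Rigor sections include the clause "and therefore warrants further testing in a future larger trial". In both places it is loosely attached to a sentence about testing feasibility, and is too weak to carry that inference.
- A reader might infer that missing 80% must block or reshape a later trial. The plan uses the criteria to judge feasibility and adopts no such go/no-go rule.

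**Conclusion.** The point holds in a limited form. The planned p-value for retention does not show whether the 80% criterion was met, because the test is non-directional, no decision rule is attached to it, and at 30 dyads it does not separate most results that miss the criterion from most that meet it. The size is a non-significant band of 20 to 28 retained, on three assumptions: a one-sample chi-square, a two-sided 0.05 level and 30 dyads in the denominator. Other reasonable choices move the edges by a dyad or so without removing the problem. Results of 19 or fewer and 29 or more are distinguished from 80%, and the observed rate will be reported in any case. The efficacy hypotheses, the sample size and participant safety are unaffected. Severity is minor to moderate.

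**What to change.** In Data Analysis, remove the chi-square test for retention and state three things:

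- The criterion is judged on the observed proportion and is met if at least 80% of all enrolled dyads are retained (24 or more if 30 are enrolled).
- The sponsor's definition of the retention endpoint. Possible anchors in the protocol include the second study visit and the dispensing records obtained 3 months after it. The sponsor should also say how dyads brought in from the waitlist count in numerator and denominator.
- The proportion is reported with an exact (Clopper-Pearson) 95% confidence interval.

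The cost is wording only, with no extra data or visits. The plan should disclose the downside. With about 30 dyads the rule is met with probability only 0.61 when true retention is exactly 80%, and still 0.35 at 75% and 0.16 at 70%. The interval will be wide (61% to 92% at 24/30). The verdict is therefore a benchmark on the point estimate and should not be presented as proof of the true retention rate.
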